Transepical With Transseptal Autologous CD 133+ Bone Marrow Cell Implantation in Patient Following CABG Surgery

ClinicalTrials.gov ID: NCT02870933

Date: February 25th, 2020

Study Protocol

Objectives

Numerous publications in the last decade have been conducted to study the effect of stem cell therapy in improving cardiac function, but the results and the type of cell and implantation procedure vary considerably. The CD133+ bone marrow cell has been shown to possess a high angiogenesis capacity. One previous study published by Nasseri et al. reveals that trans-epicardial implantation of CD133+ for low LVEF patients who underwent CABG showed no significant improvement; nevertheless, it is stated that this result might differ if the trans-septal region is included as a site of stem cell implantation. Therefore, we perform a randomized clinical trial at our Department of Cardiovascular Surgery of National Cardiovascular Center Harapan Kita, Indonesia, and include additional trans-septal implantation of CD133+ to assess the impact of stem cells in improving cardiac function.

Design and Methods

This study was conducted between March 2016 and June 2018, and the study had been approved by the Institutional Review Board and Ethics Committee of National Cardiovascular Centre Harapan Kita (No. LB.02.01/VII/086/KEP.007/2016) and Universitas Indonesia (No:999/UN2.F1/ETIK/XI/2016). This study had also been registered on ClinicalTrial.gov (**NCT02870933**). All patients enrolled in this study had been informed about the procedures and signed the written informed consent. Thirteen patients were randomized and assigned to

each group. Patients in the case group received CABG + implantation of CD133+, and the control group received a CABG-only procedure.

Inclusion criteria for this study were as follows: i) aged <70, three vessels with coronary artery disease, and indication for coronary artery bypass graft (CABG) surgery; ii) impaired resting global LVEF < 35% with hypoperfused myocardium and abnormal septal wall motion were assessed by cardiac MRI; iii) hypoperfused resting state of LV on MRI. Exclusion criteria were those with i) CAD with valvular disease requiring concomitant valve surgery; ii) acute myocardial infarction; iii) a contraindication for MRI or bone marrow cell (BMC) aspiration procedure; iv) a history of ventricular arrhythmia (\geq Lown III); v) coagulation disorders, including familial hemophilia, sign/symptoms of bleeding disorders, platelets < 80000 mL; vi) chronic obstructive pulmonary disease (COPD); vii) infectious diseases (HIV, Hepatitis B, and HCV); viii) abnormal liver function and renal function test; ix) ventricular conduction disorders; x) electrolyte imbalances; xi) history of immunosuppressant medication, cytotoxic agents, and radiotherapy within four months before date of surgery.

The minimum of 13 patients per group was required to show the inter-group difference in LVEF, with a power (b) of 80% at a two-sided a level of = 0.05. However, 15 patients in each group were included for dropout anticipation.

Bone Marrow (BM) Aspiration

Bone marrow aspiration was done 24 hours before the scheduled CABG. Patients were anesthetized locally, and aspiration was carried out from the posterior iliac crest. A specimen of 190–210 mL of BM volume was harvested and diluted with 25 mL of normal saline containing 40,000U heparin.

CD133+ Separation Process

The aspirate was then transferred to our stem cell facility. Phosphate buffer saline was added until a total volume of 450 mL was reached and then centrifuged to dispose of the platelet. 1.5 mL of Magnetic MicroBeads[®] anti-CD133 labeling (Miltenyi Biotec) were added and incubated at room temperature for 30 minutes. Separation of the CD133+ was conducted using the *CliniMACS*[®] Magnetic Separation Device (Miltenyi Biotec). The final product was stored at 4–8 °C. The final aspirate volume for implantation was 20 mL, with a CD133+ count ranging from 5–10 million cells. Ten-mL samples were drawn to assess cell numbers, proof of sterility, purity, and the viability of the CD133+ using flow-cytometry FACS Aria III (BD Biosciences). The volume of the initial BM was 190–210 mL. The purity of the CD133+ end-product was 84.4–90.1%, with the viability of 95.2–94.4%.

Surgery

Anesthesia and CABG surgery was carried out according to the regular surgical protocol. The CD133+ was prepared in 20 one-mL syringes with 25G needles (0.5 x 25mm). Trans-septal implantation of CD133+ was performed by going along the left anterior descending artery (LAD). The correct needle placement within the interventricular septum was assessed with the use of trans-oesophageal echocardiography. Each injection of 0.5 mL of CD133+ was administered at injection sites approximately 1.0 cm apart. Ten injections were administered in the trans-septal region, and the other 30 injections were injected along the border area of the hypo-kinetic/hypo-perfused segment, which had been identified by MRI or by visible scarring area and epicardial muscles discoloration.

Cardiac magnetic resonance imaging and analysis

All patients were assessed at the same imaging facility in our hospital before the surgery and six months after the procedure. Our imaging facility was equipped with a Philips Achieva 1.5T

MRI. All subjects underwent resting and stress (adenosine 140 µg/kg/min) MRI with contrast agent *gadopentate dimeglumine* (0.05 mmol/kg). Left ventricular ejection fraction (LVEF), scar size, and wall motion score index (WMSI) were analyzed using *software cvi42*®.

Quality of life and aerobic capacity

The Minnesota Living with Heart Failure Questionnaire (MLHFQ) and the six-minute walk test (6MWT) were used to evaluate the quality of life and the aerobic capacity before and six months after the procedure. Registered cardiologists assessed the 6MWT for all patients recruited. The Minnesota Living with Heart Failure Questionnaire (MLHFQ) consisted of 21 questions that were used to assess the quality of life.

Statistical Analysis Plan (SAP)

All statistical data were analyzed using *IBM SPSS Statistics version 21.0 (SPSS Inc, Chicago, IL, USA)*. Continuous data were presented as mean \pm standard deviation or median and interquartile range; categorical data were presented as number (n) and percentage. Shapiro-Wilk's test was utilized to assess the distribution of the data. Data were analyzed with independent t-test or Mann Whitney test accordingly. The measurement of scar size proportion presented as improved and non-improved categorical data were compared by the Chi-square test. In all cases, *the P-value* of < 0.05 was considered statistically significant. All of our results were measured by comparing the pre- and post-intervention changes of both groups. Data on boxplot were presented in median and minimum-maximum. Especially, statistical analysis in changes LVEF variable and changes in WMSI used paired t test, analysed defect segment perfusion, MLHFQ and the 6MWT we used Mann-Whitney test and scar size proportion we used chi-square test.

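### The only SAP text is dated about 20 months after the study period, so its tests and scar split are not shown to be pre-specified and a 5% error rate cannot be assumed

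*Combined protocol and SAP*

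**What the plan says.** The title block carries the only date in the file: "Date: February 25th, 2020". Design and Methods then reports: "This study was conducted between March 2016 and June 2018". There is no version history, no separate SAP date and no statement that the analysis was fixed before outcome data were seen.

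The text reports finished work. Design and Methods describes randomisation as done ("Thirteen patients were randomized and assigned to" each group). The CD133+ Separation Process section gives an observed result: "The purity of the CD133+ end-product was 84.4–90.1" percent.

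The SAP section first sets a conditional rule: a Shapiro-Wilk check, then an independent t-test or Mann-Whitney test. It ends with a fixed list. Changes in LVEF and WMSI get a paired t test; for the rest it says "analysed defect segment perfusion, MLHFQ and the 6MWT we used Mann-Whitney test and scar size proportion we used chi-square test". Scar size is divided into improved or not improved, with no threshold given. Every test is judged at P<0.05.

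LVEF is singled out only in the sample-size paragraph: "The minimum of 13 patients per group was required to show the inter-group difference in LVEF, with a power (b) of 80" percent, at a two-sided 0.05 level. No endpoint is called primary.

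**The concern.** A test or category split keeps its nominal error rate only if it was fixed without sight of the outcomes. Here a rule that depends on the data's distribution is followed by a list saying which test each endpoint received. A forward-looking plan could not know the Shapiro-Wilk results, so the list reads like the rule's outcome on observed data. A split with no stated cut-off cannot be checked against any earlier intention.

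Posted as an analysis plan, the text invites readers to treat every P<0.05 among six endpoints as a planned finding. At stake is which results, if any, can be called confirmatory.

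**Working it through.** **Timing.** From 30 June 2018 to 25 February 2020 is 19.9 months; from 1 June 2018 it is 20.8. The document does not say whether June 2018 includes the last six-month visit (imaging took place "before the surgery and six months after the procedure"). If June 2018 was instead the last operation, follow-up ended in December 2018, and 19.9 − 6 = 13.9 months still remain. On either reading the document postdates the outcome data.

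**The plan's own figure.** The 13 per group cannot be reproduced, because no LVEF difference or SD is given. Solving backwards with n = 2(1.96 + 0.84)²/d² gives d = 2.80 × √(2/13) ≈ 1.10 SD (1.15 with the t distribution). The planned 13 also equals the number reported as randomised per group, while the sample-size paragraph adds "However, 15 patients in each group were included for dropout anticipation". The sentence is therefore not independent evidence of a prior plan.

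**Six endpoints.** LVEF, WMSI, perfusion defect, MLHFQ, 6MWT and scar size, each tested between arms at 0.05 under no effect:
- independent: 1 − 0.95⁶ = 26.5%
- assumed pairwise correlation 0.3, 0.5, 0.7 (simulated): about 24%, 21%, 16%

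**t-test or Mann-Whitney.** Null simulation, 20,000 trials, 13 per arm, taking the smaller P:
- normal data: t 5.1%, Mann-Whitney 4.5%, smaller of the two 5.8%
- skewed (lognormal) data: 3.5%, 4.4%, 5.6%

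Free choice between the two costs less than 1 point above 5%. If the Shapiro-Wilk rule is followed (assuming Mann-Whitney whenever either arm fails at 0.05), the rate is 4.7% for normal and 5.2% for exponential data.

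**Scar split.** Assumptions: no effect, 13 per arm, normal changes, candidate cuts at a reduction of 0, 0.25 or 0.5 SD.
- One fixed cut at 0, uncorrected chi-square: about 7.5%. Exact check: sum Bin(a; 13, 0.5) × Bin(b; 13, 0.5) over all tables with P<0.05, which gives 7.6%.
- Best of the three cuts, uncorrected: 13.0–13.5% across runs.
- Best of the three cuts, continuity-corrected: 5.3–5.4%; Fisher's exact test: 5.4–5.5%.

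The SAP does not say which form of chi-square is meant. If uncorrected, roughly 2.5 points of the excess over 5% come from the small sample even at one pre-specified cut (7.5 − 5); the other 6 or so come from choosing the cut (13.5 − 7.5).

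**LVEF test.** The sample size rests on a difference between groups. A paired t test compares before with after inside one arm. If both arms improve equally by an assumed 0.3, 0.5 or 0.8 SD of change, the cell arm is significant and the control arm is not in 14%, 24% or 18% of simulated trials. A within-arm reading therefore cannot stand in for the comparison the trial was sized on.

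**The case against.** The date belongs to a combined file, not to each decision in it. Design and Methods cites two ethics approvals and a registration, any of which may hold earlier analysis text. A reader might infer that the tests were chosen after seeing the results, or that the true error rate is known to exceed 5%. The documents support neither. They show only an absence of evidence for pre-specification, and the true rate is unknown. That objection stands and sets the wording of this point.

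A reader might also add freedom to test final values instead of changes, which raises the simulated rate to about 10%. The SAP says results compare changes between groups, so that option is not open on its text. The scar cuts are assumed, and improved may simply mean any reduction; with a continuity correction, choosing among three cuts shows almost no inflation above 5%.

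Finally, a reader might treat the LVEF comparison as proven to be planned because a sample size has to precede enrolment. The sentence sits in the same 2020 text, gives no difference or SD, and is followed by a paired t test in the SAP. It is the best-supported candidate, no more.

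What remains is that nothing in the file lets a reader separate planned from later choices, and that six endpoints share an unadjusted 0.05 with no primary.

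**Conclusion.** The point holds as a failure to show pre-specification. The 5% rate cannot be assumed across the six endpoints. The main exposure is the unadjusted set: about 16–27% chance of at least one false positive for correlations from 0.7 down to 0, assuming one two-sided between-arm test per endpoint, each at exactly 5%. The scar split ranges from about 5.4% to about 13.5% for the best of three assumed cuts, depending mainly on which chi-square was used. The choice between t-test and Mann-Whitney is not a material problem. All simulated rates rest on assumed distributions, correlations and cuts; they illustrate the exposure and do not describe what the investigators did.

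**What to change.** - State in the SAP when it was written relative to data collection and analysis.
- Supply any dated earlier protocol, SAP or ethics text and list every departure from it. Check its date against the March 2016 start: one approval number contains XI/2016, which may mean November.
- If no such text exists, name one main comparison: the between-arm difference in LVEF change, by an independent-groups test at two-sided 0.05, in line with the sample-size sentence and in place of the paired t test. Describe it as the best-supported planned analysis, not as independently documented.
- Label WMSI, perfusion, MLHFQ, 6MWT and scar size exploratory.
- State the scar cut-off and the form of chi-square, and print the continuous between-arm scar change beside the split.

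The cost is wording and a few extra rows of output from existing data. The downside is that the secondary results lose confirmatory status. If a dated earlier plan exists, producing it answers the timing question for whatever it specifies.

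### Scar size, measured on MRI before surgery and at six months, is reduced to an undefined improved/non-improved split and tested by chi-square, discarding the size of the change and losing power

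*Combined protocol and SAP*

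**What the plan says.** The section on cardiac MRI in the protocol gives the timing for every patient: "All patients were assessed at the same imaging facility in our hospital before the surgery and six months after the procedure". It groups scar size with two other imaging measurements: "Left ventricular ejection fraction (LVEF), scar size, and wall motion score index (WMSI) were analyzed using" a named software package.

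The SAP sets a general rule: "All of our results were measured by comparing the pre- and post-intervention changes of both groups". For scar it then states: "The measurement of scar size proportion presented as improved and non-improved categorical data were compared by the Chi-square test". Its closing sentence repeats the choice: "scar size proportion we used chi-square test".

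That sentence assigns a t test to the changes in LVEF and wall motion score index, and Mann-Whitney to perfusion defect segments, the quality-of-life score and the walk test. Scar is the only one of these outcomes reduced to two categories. The SAP gives no reason for this, and no section defines improvement by a threshold, a minimum change or a rule for no change.

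**The concern.** There are two separate problems.

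- **Undefined endpoint.** The chi-square P-value depends on where the line between improved and non-improved is drawn, and that line is not written down. A reader cannot reproduce the classification, or rule out that the line was chosen after the data were seen. This problem needs no power assumption.
- **Lost information.** Once each patient is reduced to yes or no, a difference within measurement error counts as much as a large reduction. With 13 to 15 patients per arm there is little information to spare, and a real scar reduction is more likely to be missed.

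The SAP's own rule of comparing pre-to-post changes between groups would be met more fully by analysing the change itself, as it does for the other MRI outcomes.

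**Working it through.** **Inputs from the documents.** The sample-size paragraph says "The minimum of 13 patients per group was required to show the inter-group difference in LVEF". The error rates it states are 80% power and a two-sided α of 0.05. Fifteen per group were included to allow for dropout. The SAP sets significance at P < 0.05. No effect, SD or improvement rate is given for scar.

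**The plan's own figure.** The 13 per group cannot be reproduced, because no LVEF difference or SD is stated. It can only be inverted to a standardised effect d:

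- Normal approximation: d = (1.960 + 0.842) × √(2/13) = 1.10.
- Two-sample t test (noncentral t, 24 df, noncentrality d × √(13/2)): 80% power at d = 1.145.

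**Assumptions for the comparison.** Scar change is normal with equal SD in both arms. The shift is d = 1.145, or a smaller d = 0.8. The control improvement rate p₀ is 0.16, 0.28, 0.38, 0.50 or 0.62. The treated rate follows as p₁ = Φ(Φ⁻¹(p₀) + d). For example, p₀ = 0.50 and d = 1.145 give p₁ = Φ(1.145) = 0.874.

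**Method.** Chi-square power is the sum of the binomial probabilities of every 2×2 table with an uncorrected Pearson statistic above 3.841, by full enumeration. The t test uses the noncentral t distribution. Mann-Whitney uses its exact null distribution and 8,000 simulated trials.

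Power of chi-square on the split outcome, by control improvement rate:

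| n per arm | d | 0.16 | 0.28 | 0.38 | 0.50 | 0.62 |
|---|---|---|---|---|---|---|
| 13 | 1.145 | 64% | 70% | 67% | 59% | 47% |
| 13 | 0.8 | 33% | 42% | 43% | 38% | 30% |
| 15 | 1.145 | 66% | 67% | 67% | 64% | 56% |
| 15 | 0.8 | 37% | 39% | 39% | 39% | 36% |

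Power when the measured change is analysed:

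| n per arm | d | t test | Mann-Whitney |
|---|---|---|---|
| 13 | 1.145 | 80% | 77% |
| 13 | 0.8 | 50% | 46% |
| 15 | 1.145 | 86% | 83% |
| 15 | 0.8 | 56% | 53% |

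**Loss against Mann-Whitney at 13 per arm.**

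- d = 1.145: 76.9 − 69.7 = 7 points at best, and 76.9 − 47.2 = 30 points at worst.
- d = 0.8: 45.6 − 43.1 = 3 points (2.5 before rounding), and 45.6 − 30.2 = 15 points.

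**Sample size for 80% power.** At d = 1.145 the chi-square first reaches 80% at 18 to 26 per arm, against 13 for a t test. The 18 is a first crossing (p₀ = 0.28): power dips below 80% again and stays above it only from 21. At d = 0.8 the requirement is 39 to 48 per arm, against 26 for a t test.

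**True size of the chi-square test.** With both arms improving at a common rate of 10%, 20%, 30%, 40% or 50%, the uncorrected test at 13 per arm rejects in 1.8%, 4.3%, 5.7%, 7.0% or 7.6% of trials. At 15 per arm the maximum is 5.5%. The test is conservative when few improve, mildly liberal at 13 per arm when about half improve, and close to nominal at 15.

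**The case against.** The strongest reply is that the premise and the power figures are both softer than they look.

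- **Scale.** The documents never say outright that scar proportion is continuous. It could be scarred segments over all segments, with few distinct values and many zero changes. *This stands as a caution:* the normal-shift figures would not then apply directly. A graded proportion would still lose information when cut in two.
- **Borrowed effect.** The shift of 1.145 comes from the LVEF sample size, and nothing links it to scar. At 0.8 the recommended Mann-Whitney also misses the effect more often than not, and the smallest loss is only 3 points. *This stands:* small numbers are a large part of the weakness, and splitting adds to it.
- **Ranges are not bounds.** They depend on the control rates tried. *This is correct.* At 13 per arm and d = 1.145, chi-square power is 54% if 10% of controls improve and 37% if 70% do.
- **Plain reading.** Improved may simply mean any decrease. *That is possible but unwritten.* Even then, a one-line definition would cure only the first problem, because the amount of change would still be discarded.
- **Importance.** Scar is a supporting outcome and any replacement analysis is now post hoc. *Both are true*, and they limit the weight of the point without removing it.

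**Conclusion.** The concern holds. Two facts rest on the text alone: the SAP commits scar size to a two-category chi-square, stated twice, and no definition of improved appears anywhere. Scar is also singled out, since the other MRI outcomes are tested unsplit.

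Power was lost in every scenario tried. At 13 per arm the loss against Mann-Whitney is 7–30 points at d = 1.145 and 3–15 points at d = 0.8. Its size rests on assumed normal, equal-SD changes, assumed shifts and assumed control improvement rates. That scar proportion is a measured quantity is inferred from its name and from its listing with LVEF and wall motion score index.

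The main fault is lost information and an unstated cut-off, not a generally invalid P-value. The point should be addressed, but it affects neither the LVEF sample size nor the LVEF analysis.

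**What to change.** - **Main scar analysis:** compare scar proportion between groups on its measured scale, either as the six-month value adjusted for baseline or by Mann-Whitney on the change, which the SAP already uses for perfusion defect. Report the between-group difference with a 95% confidence interval.
- **Improved/non-improved:** keep it as a descriptive table, with the threshold and the handling of unchanged scar written out.
- **If the split is still tested:** use an unconditional exact test (Barnard or Boschloo). At 13 per arm, 3 v 8, 4 v 9 and 5 v 10 improved are significant by chi-square but not by Boschloo (P = 0.061, 0.076 and 0.061). Exact testing costs further power: at d = 1.145 Boschloo has 47–58% and the very conservative Fisher test 30–54%. The measured change should therefore carry the inference.
- **Labelling:** the study ran to June 2018 and the document is dated February 2020, so mark the new analysis as post hoc and show it beside the chi-square result.

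The cost is a change of SAP wording and a rerun on data already collected, provided the measured scar values were kept. The display becomes slightly less simple.

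### The SAP's only inference for any outcome is P < 0.05, with no between-arm difference or confidence interval, although at 13 per arm the 95% interval spans about ±0.81 SD

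*Combined protocol and SAP*

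**What the plan says.** The Statistical Analysis Plan (SAP) is one paragraph. It provides for:

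- **Summaries:** mean with SD or median with interquartile range for continuous data, number and percentage for categorical data, and boxplots ("Data on boxplot were presented in median and minimum-maximum").
- **Tests:** independent t or Mann-Whitney in general. The closing sentence then assigns a paired t test to the changes in LVEF and WMSI, Mann-Whitney to perfusion-defect segments, MLHFQ and 6MWT, and chi-square to scar size (improved or not improved).
- **Decision rule:** for all outcomes, a P-value "of < 0.05 was considered statistically significant".

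It also says that results rest on comparing the two groups' changes from before to after the intervention. No estimate of the difference between groups, and no interval around one, is mentioned there or elsewhere in the document.

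The sample-size paragraph under Design and Methods says "The minimum of 13 patients per group was required to show the inter-group difference in LVEF". The power claimed for this is 80%, with alpha 0.05 on two sides. It gives neither the size of that difference nor an SD. It adds: "However, 15 patients in each group were included for dropout anticipation". An earlier paragraph of the same section says that thirteen were randomised to each group.

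**The concern.** The stated objective is to assess the impact of the cells on cardiac function, which is a question of size. A P-value does not answer it. A Mann-Whitney or chi-square P-value carries no magnitude, and a paired t test run within each arm tests change from baseline, which includes whatever CABG alone achieves. As written, the plan could be followed in full without producing the quantity the trial was set up to estimate: how much more the CD133+ arm changed than the control arm, and how precisely that is known.

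In a large trial this would mainly be a reporting gap. With 13 to 15 per arm it affects what can be concluded. Many results short of significance would be compatible with both no benefit and a large benefit, and many significant results would be compatible with a benefit anywhere from slight to very large.

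**Working it through.** **Inputs from the document.** Two-sided alpha 0.05, power 80% and 13 per group (15 with the dropout allowance), from the sample-size paragraph. Two parallel arms.

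**Not in the document.** The LVEF difference and the SD. The stated 13 per group therefore cannot be reproduced forwards. It can only be solved backwards, in SD units of the analysed change, assuming an independent two-sample t test with equal arms.

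**1. Detectable difference at 80% power.**
- Normal approximation: d = (z₀.₉₇₅ + z₀.₈₀) × √(2/n) = (1.960 + 0.842) × √(2/13) = 2.802 × 0.3922 = 1.10 SD. At 15 per arm: 2.802 × 0.3651 = 1.02 SD.
- Noncentral t (df = 2n − 2, noncentrality d√(n/2)): 1.145 SD at 13 per arm and 1.06 SD at 15 per arm.
- For the Mann-Whitney outcomes, assuming normal data and relative efficiency 3/π: about 1.17 SD at 13 per arm.

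Thirteen per group is thus consistent with a planned difference of roughly 1.1 SD, but the document does not say that this was the assumption.

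**2. Power for smaller true differences (noncentral t).**

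| True difference | 13 per arm | 15 per arm |
|---|---|---|
| 0.5 SD | 23% | 26% |
| 0.8 SD | 50% | 56% |
| 1.0 SD | 69% | 75% |

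**3. Half-width of the 95% confidence interval**, t₀.₉₇₅ × √(2/n), in pooled SDs.
- 13 per arm: 2.064 × 0.3922 = 0.81 SD.
- 15 per arm: 2.048 × 0.3651 = 0.75 SD.

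**4. What this means for reading a result at 13 per arm.**
- Observed difference 0.5 SD: interval 0.5 ± 0.81, or −0.31 to 1.31 SD. Not significant, yet compatible with the 1.145 SD the trial can detect.
- Observed difference 0.1 SD: interval −0.71 to 0.91 SD. Also not significant, but 1.145 SD is excluded.
- Observed difference 0.9 SD: interval 0.09 to 1.71 SD. Significant, but anything from a slight to a very large benefit remains possible.

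The first two results get the same verdict under P < 0.05. Only the interval separates them. The dividing point is 1.145 − 0.81 = 0.335 SD: a non-significant observed difference between about 0.34 and 0.81 SD leaves both zero and 1.145 SD inside the interval.

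**5. In LVEF points**, for an assumed SD of change of 5, 8 or 12 points (an assumption; the document gives none), at 13 per arm:
- Half-width: about ±4.0, ±6.5 or ±9.7 points.
- Difference with 80% power: about 5.7, 9.2 or 13.7 points.

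**6. The paired t test.** None of these figures applies to a within-arm paired test. If the closing sentence of the SAP is taken literally, the LVEF analysis does not address the inter-group difference on which the sample size was based.

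**The case against.** **The summaries may suffice.** If changes are reported as mean, SD and n, a reader can work out the mean difference and its interval. The same holds for scar from numbers and percentages. This has some force: P < 0.05 is the only inference planned, not the only output. But the plan does not commit to summarising the changes in this form, and a Hodges-Lehmann shift with its interval cannot be recovered from medians and interquartile ranges.

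**A reader might infer that a null result will be read as no effect.** The document does not support that. It contains no such rule. The Objectives do describe the earlier trial by saying that implantation "for low LVEF patients who underwent CABG showed no significant improvement", but the same sentence goes on to suggest that the result could differ with septal injection. The authors did not treat that null as settled.

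**A reader might infer that 13 per group is too few.** That is not shown either. Any trial powered at 80% has less power below its design effect. With no difference or SD stated, 1.15 SD cannot be called implausible, so the sample size is unverifiable, not wrong.

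**A reader might infer that significant estimates would be doubled.** In simulation, significant results average about twice the truth only if the true difference is as small as 0.5 SD. The ratio falls to about 1.4 at 0.8 SD, 1.2 at 1.0 SD and 1.1 at 1.145 SD. The two-fold figure depends on a chosen effect size. An interval would disclose the imprecision but would not remove this selection effect.

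**The number analysed is unclear.** Using 15 per arm in place of 13 moves the figures slightly and leaves the conclusion unchanged.

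**Conclusion.** The point holds in this form. The plan's only inference for every outcome is a P-value at 0.05, no between-arm difference or interval is planned, and the test named for LVEF and WMSI does not, on its literal wording, compare the arms. The interval that is missing would be wide: about ±0.81 SD at 13 per arm or ±0.75 SD at 15, with 80% power only for about 1.15 SD or 1.06 SD. A non-significant result can therefore be misread as no effect, and a significant one would carry no statement of its imprecision.

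The SD-unit figures rest on the stated alpha, power and group sizes, and on an independent two-sample comparison of changes with equal arms. Conversion to LVEF points rests on an assumed SD. The finding concerns how results are estimated and reported. It does not show that the sample size was wrong or that any conclusion will be mistaken.

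**What to change.** **In the Statistical Analysis Plan (SAP):** for each outcome, report the between-arm difference in change from before surgery to six months, with a 95% confidence interval:

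- LVEF and WMSI: mean difference from the independent-groups comparison. This also settles the role of the paired t test, which could remain as a within-arm description.
- Perfusion-defect segments, MLHFQ and 6MWT: Hodges-Lehmann shift.
- Scar improvement: difference in proportions.

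Base the conclusion on the estimate and its interval, not on P < 0.05 alone.

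**In the sample-size paragraph:** state the LVEF difference and SD that the sponsor actually assumed. A back-solved 1.15 SD should not be written in as though it had been the assumption, because 13 per group also follows from 1.10 SD by the normal approximation. For the same reason, this point proposes no rule that calls a result inconclusive unless the interval excludes the sizing difference, since that difference is not given.

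**Cost:** a few sentences of SAP text and some extra output from measurements already planned. No additional patients, visits or measurements are needed.
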